In a study conducted in our country, the mean quality of life score in children with celiac disease was found to be 69.1 ± 17.1 (49). According to this value, it was determined in the study that after the support program, it was aimed to increase the effect size of the quality of life scores by 0.8 (increase the quality of life from 69.1 ± 17.1 points to 82.8), and it was determined that at least 15 people should be included in the experimental group in calculating the sample number with 5% alpha error margin and 80% power. (G * Power 3.1.9.2). Considering the possible loss of patients, it was decided to enroll a total of 36 patients, 18 patients in the experimental group and 18 patients in the control group, with an excess of 10%.

Working groups will be assigned to the experimental and control groups by randomization by lot method.

1.4. Type of the study: The research was experimentally planned with pre-test, post-test control group.

1.5. Required manpower for research:

[name]. [name]: Coordinator of the research (creation of the method, follow-up of the application, evaluation of the findings, management of possible problems)

Lecturer . [name]: She will take part in the stages of obtaining institution and ethical approvals, implementation, data collection, data entry, interpretation and evaluation of study findings. In this process, information will be shared with the researcher.

Assoc. [name] [name]: She will contribute to the stages of obtaining patient records, sharing patient information and directing patients for application.

1.4. Research method and data collection tools:

Peer interactive group training will be applied for 3 months, one week apart, and will consist of 6 sessions in total. Support group meetings were planned to be held at the weekend in order to prevent adolescents' attendance at school. Adolescents will be contacted by phone before each session, and will be invited by informing about the date and time of the meeting. Each session will continue for 1.5 to 2 hours.

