Adolescents to be included in the control group will be administered an Introductory Information Form for Adolescents with a diagnosis of Celiac disease, the Quality of Life Scale for Children, the Peer Relations Scale, and the Coping Scale for Adolescents in the outpatient clinic in order to compare the effect of education in the hospital routine and peer interactive group support. After three months, the Adolescents in the control group will be re-administered the Quality of Life Scale for Children, the Peer Relationship Scale, and the Adolescent Coping Scale.

First Session; In this session, adolescents will be provided to share their knowledge of the disease. "What is celiac?", "What are the symptoms of celiac?" , "What does the celiac treatment include?" questions will be asked. By enabling adolescents to discuss among themselves, sharing of information, completing the missing information by the researcher and correcting the wrong information will be provided. In this session, Introductory Information Form, Children's Quality of Life Scale, Peer Relationship Scale, Adolescent Coping Scale will be applied to Adolescents with Celiac Diagnosis.

Second Session; In this session, to enable adolescents to share their difficulties with the disease, group members,

1- "How do you perceive living with celiac disease?"

2- "How is it an experience to live with celiac disease?", "How did celiac disease affect your life?"

3- "What are the difficulties you experience in daily life?"

4- "How do you deal with these problems in your daily life?", "What are the areas that you have difficulties in coping with the difficulties you experience?" questions will be asked.

Questions directed to the participants will be discussed among the group leader and participants.

The contents of the Third, Fourth, Fifth and Sixth sessions will be created regarding the problems identified in the first and second sessions. The determined problem areas will be discussed in each session. At the end of the sixth session, the Adolescents will be again applied to the Quality of Life Scale for Children, the Peer Relationship Scale, and the Adolescent Coping Scale.

After peer interactive group support, celiac patients will be given an educational booklet named "Living with Celiacs" to be created by the researcher.

In the content of the training booklet;

- What is celiac disease?
 - What are the symptoms of celiac disease?
- Celiac and life
- What is the treatment for celiac disease?

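### The experimental arm's pre-test is taken inside the first group session and the controls' in the clinic, neither is placed before the draw, and the pre-to-post interval may differ between arms

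*Combined protocol and SAP*

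**What the plan says.** **Design.** Protocol section 1.4 (Type of the study) states: "The research was experimentally planned with pre-test, post-test control group". Section 1.5 (Data analysis) compares each group's scores before and after the intervention with a paired t or Wilcoxon test. The Statistical Analysis part keeps these paired tests and gives no assessment times.

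**Experimental arm, pre-test.** Under First Session, the protocol describes adolescents discussing what celiac disease is, its symptoms and its treatment, with "completing the missing information by the researcher and correcting the wrong information will be provided". It then adds: "In this session, Introductory Information Form, Children's Quality of Life Scale, Peer Relationship Scale, Adolescent Coping Scale will be applied". The position of the forms within the session is not given.

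**Experimental arm, post-test.** Here the position is given: "At the end of the sixth session, the Adolescents will be again applied to the Quality of Life Scale for Children".

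**Control arm.** The pre-test comprises the information form, the quality-of-life and peer scales, and the "Coping Scale for Adolescents in the outpatient clinic in order to compare the effect" of hospital routine and group support. For the post-test: "After three months, the Adolescents in the control group will be re-administered".

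**Schedule.** "Peer interactive group training will be applied for 3 months, one week apart, and will consist of 6 sessions in total".

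**Randomisation.** Section 3.3 and the Statistical Analysis part describe a draw by lot. Neither says whether the pre-test comes before or after it.

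**The concern.** The first session is one of the six that make up the intervention. If the forms are filled in after its discussion, the experimental arm's before score already includes some exposure, and the paired test no longer measures change from an untreated state. Even if the forms come first, the experimental arm is measured at a group meeting, when patients know their allocation, while controls are measured at a clinic visit. The two baseline scores are then taken on different occasions, and the check that the groups start alike is weaker for it.

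The paired test matters because the sample size appears to rest on it (shown below).

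A second, separate matter is the time between pre-test and post-test. The schedule sentence gives two durations that do not agree if it is read as weekly sessions, and the controls' re-test is fixed at three months. If the arms are re-tested after different lengths of time, ordinary change over time differs between them. Because this concerns when the post-test is taken, it is not confined to the paired tests.

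**Working it through.** **1. The plan's own figure.** Inputs from Sample Number Calculation: mean 69.1, SD 17.1, target 82.8, effect size 0.8, alpha 5%, power 80%, and "at least 15 people should be included in the experimental group". Check: (82.8 − 69.1)/17.1 = 13.7/17.1 = 0.80. The test and its sidedness are not named; I take two-sided and use the noncentral t distribution.

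| Test at effect size 0.8 | n | Power |
|---|---|---|
| Paired | 14 | 0.790 |
| Paired | 15 | 0.821 |
| Paired | 18 | 0.892 |
| Two-sample, per arm | 18 | 0.645 |
| Two-sample, per arm | 25 | 0.792 |
| Two-sample, per arm | 26 | 0.808 |

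Fifteen is exactly the two-sided paired answer. A two-sided two-sample test would need 26 per arm. The study therefore appears to be sized on the test that uses the pre-test score.

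**2. What a shifted pre-test would do (illustration).** The documents give no shift, so s is assumed, in SD units of the score, and acts on the pre-test only. A positive s means a raised pre-test. With pre-post correlation r:

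- expected change = (0.8 − s) × 17.1 points
- SD of change = 17.1 × √(2(1 − r))
- standardised change = (0.8 − s)/√(2(1 − r))

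At r = 0.5 the SD of change is 17.1 × √1 = 17.1, the value at which the plan's 15 is reproduced.

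| s (SD) | Expected change (points) | Power, n = 18 | Power, n = 15 |
|---|---|---|---|
| +0.2 | 0.6 × 17.1 = 10.3 | 0.67 | 0.58 |
| +0.1 | 0.7 × 17.1 = 12.0 | 0.80 | 0.71 |
| 0 | 0.8 × 17.1 = 13.7 | 0.89 | 0.82 |
| −0.1 | 0.9 × 17.1 = 15.4 | 0.95 | 0.90 |
| −0.2 | 1.0 × 17.1 = 17.1 | 0.98 | 0.95 |

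The last two rows are not a gain: the extra change comes from a depressed starting score, not from the programme.

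Sensitivity to r, n = 18, s from 0 to +0.2: power falls from 0.77 to 0.53 at r = 0.3 (SD of change 20.2) and from 0.98 to 0.87 at r = 0.7 (SD of change 13.2).

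A setting effect that is equal at session one and session six cancels in the difference, and power stays at 0.89 (n = 18, r = 0.5). Only an effect of session-one content, or of setting on that day alone, counts.

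**3. Which analyses use the pre-test.** The within-arm paired tests and the baseline comparison of scale scores do. The between-group post-test comparison (independent t or Mann-Whitney) does not.

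**4. Interval between the two tests.** Six sessions have five gaps.

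- Read as weekly: 5 × 1 = 5 weeks.
- Read as alternate weeks: 5 × 2 = 10 weeks.
- Three months: 3 × 52/12 = 13 weeks, the controls' interval.

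Neither reading of the spacing gives 13 weeks.

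**The case against.** The strongest reply is that the intended order is clear enough. The design is labelled pre-test and post-test, the analysis section speaks of scores before and after the intervention, and where the authors mean the end of a session, as at session six, they say so. In a translated text, a missing note that forms come at the start is a gap in wording. This largely stands: a reader might infer that the pre-test is contaminated, and the documents do not support that. They leave the order open and lean towards forms first.

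Nor is a large effect likely. Session one deals with knowledge, and none of the three outcomes is a knowledge score. The quality-of-life scale asks about the last month, which one discussion can hardly change. That also stands, with the limit that no recall period is stated for the friendship or coping scales. The assumed shifts of 0.1 and 0.2 SD are 12.5% and 25% of the whole 0.8 SD target, nothing in the documents supports them, and at 18 patients the smaller one still leaves power at about 0.80.

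A reader might also infer that the arms were measured in different places or by different methods. Section 3.1 sets the whole study in one polyclinic, and the data-collection sentence describes face-to-face survey for everyone. What the documents show to differ is the occasion.

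Finally, the comparison of post-test scores between randomised groups does not use the pre-test. That is correct and limits the reach of the point. What survives is that the arrangement differs by arm, is not tied to the draw, and can be replaced cheaply by a better one.

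**Conclusion.** The point holds as a worthwhile and inexpensive improvement, not as a demonstrated bias. The experimental arm's pre-test sits inside a session with active content, the controls' is at a clinic visit, and neither is placed before the draw. Any resulting error is of unknown size and direction, is probably small for quality of life, and is confined to the paired tests and the baseline comparison. The power figures (0.89 falling to 0.80 or 0.67, or rising to 0.95 or 0.98) rest on an assumed shift, r = 0.5, 18 patients and a two-sided 5% test. They show sensitivity only. If the forms come first and the occasion itself has no effect, nothing is lost.

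The interval is a separate inconsistency. Depending on how the schedule is read, the experimental arm's pre-to-post interval is about 5, 10 or 13 weeks, against 13 for controls. The passages must be reconciled; the documents do not settle which reading is meant.

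**What to change.** 1. Have all 36 patients complete the information form and the three scales individually at a clinic contact before lots are drawn, and delete the pre-test from the first session. Cost: possibly one extra attendance for the 18 experimental patients, which is a real burden, since sessions are set at weekends because of school. The quality-of-life scale takes about 5 to 10 minutes; times for the other forms are not given. No new instrument is needed.
2. At minimum, add one sentence stating that the forms are completed individually before any session-one content, and report the differing occasion as a limitation of the paired tests and the baseline comparison. This needs no extra attendance.
3. The Statistical Analysis part is written in the past tense. If data are already collected, report the order and occasion actually used in each arm.
4. Separately, reconcile the three-month duration, the one-week spacing and the six sessions with the controls' three-month re-test, and use the same pre-test to post-test interval in both arms. This calls for a change of wording and timing, not an additional post-test.

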1.5. Data analysis: In the evaluation of the data of the study, the number,%, mean and standard deviation will be given in descriptive statistics. Compliance of numerical data to normal distribution will be evaluated with Kolmogorow-Smirnow test. The homogeneity of the descriptive characteristics of the experimental and control groups will be evaluated with the Chi-square test for categorical variables, and parametric or nonparametric tests according to the normal distribution in numerical variables. In comparison of the scale scores (dependent variable results) of the two groups, dependent groups t test or Mann Whitney U test will be used according to the normal distribution feature. The scale scores of the groups before and after the intervention will be compared with the dependent sample t test or the wilcoxon test. Significance level will be accepted as $p < .05$.

References

1. WHO. Global status report on noncommunicable diseases 2014: attaining the nine global noncommunicable diseases targets; a shared responsibility. Global status report on noncommunicable diseases 2014: attaining the nine global noncommunicable diseases targets; a shared responsibility 2014.
3. Wise PH. The future pediatrician: the challenge of chronic illness. *The Journal of pediatrics*. 2007;151(5):S6-S10.
4. Theofanidis D. Chronic Illness In Childhood: Psychosocial Adaptation And Nursing Support For The Child And Family. *Health Science Journal*. 2007(2).

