Statistical analyzes were performed using a package program called SPSS (IBM SPSS Statistics 24). Frequency tables and descriptive statistics were used in the interpretation of the findings. In the analysis of all tests, p value <0.05 was considered statistically significant. The homogeneity of variances was evaluated by the "Levene test" and the conformity of the study data to normal distribution was evaluated by the "Shapiro-Wilk" test. According to this; "frequency distributions (number and percentage)" are given for independent variables.

"Independent Sample-t" test (t-table value) for comparing two independent groups for normally distributed data; "Paired Sample" test (t-table value) statistics were used in the comparison of two dependent groups. "Mann-Whitney U" test (Z-table value) in comparison of two independent groups for data that do not show normal distribution; "Wilcoxon" test (Z-table value) statistics were used to compare two dependent groups.

"Pearson correlation" analysis was used to examine the relationship between the mean scale of the two groups. Correlation coefficient; It has been accepted that there is a high relation between 0.70-1.00, a medium relation between 0.30-0.70, and a low level between 0.00-0.30

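### The experimental post-test is tied to session six, with no route to retest absentees, so outcome loss may differ between arms and bias the comparison by an unknown amount

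*Combined protocol and SAP*

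**What the plan says.** Protocol section 1.4 (Research method and data collection tools) describes outcome collection separately for each arm.

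- **Experimental arm.** The pre-test is done in the first session. For the post-test: "At the end of the sixth session, the Adolescents will be again applied to the Quality of Life Scale for Children", together with the peer-relationship and coping scales. No other post-test occasion is given.
- **Control arm.** The pre-test is done in the outpatient clinic. For the post-test: "After three months, the Adolescents in the control group will be re-administered the Quality of Life Scale for Children", with the same two further scales. The place and procedure of the retest are not stated.
- **Contact.** The only contact described between assessments is the invitation to sessions: "Adolescents will be contacted by phone before each session, and will be invited by informing about the date and time of the meeting". No follow-up of absentees is described. Data are collected face to face.

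The Sample Number Calculation expects some loss ("Considering the possible loss of patients") and enrols 18 per arm. It does not split the loss by arm or link it to attendance.

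Protocol section 1.5 (Data analysis) and the Statistical Analysis part name t, Mann-Whitney, paired t and Wilcoxon tests. Neither defines an analysis set or says what happens when a post-test is missing. The only missing-data rule, in the description of the quality-of-life scale, concerns unanswered items within a questionnaire.

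**The concern.** In one arm, giving a post-test score means being present at a particular weekend group meeting. In the other it is not tied to any part of a programme. If the adolescents who stop coming differ in quality of life, peer relations or coping from those who stay, the experimental mean is taken over a selected subset of the randomised arm.

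That link is credible here. The protocol's rationale describes social isolation and adaptation problems in these patients, and the intervention is a peer group. Credible is not the same as shown, because the documents give no data on attendance.

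Two things are at stake. The between-group comparison may lose the protection of randomisation. The question answered may also drift from the effect of offering the programme to the effect among those still attending at its end. With 18 per arm, each missing adolescent is 1/18 = 5.6% of an arm, and a score that was never collected cannot be recovered at analysis.

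**Working it through.** **Inputs from the documents.** Mean 69.1, SD 17.1, target 82.8, effect size 0.8, alpha 5%, power 80%, 15 required, 18 + 18 enrolled, 10% allowed for loss.

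**The plan's own figures.** Target gain: 82.8 − 69.1 = 13.7 points, and 13.7/17.1 = 0.80. The stated 15 is reproduced by a two-sided paired t test (power 82.1% at n = 15). A two-sided two-group t test would need 26 per arm; that is a separate issue. Ten per cent of 18 is 1.8, so about 2 lost. Falling from 18 to the plan's 15 means 3 lost.

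**Assumed, because the documents give no figure.** The number m of the 18 experimental adolescents not retested; how far non-attendance is related to outcome; and control loss.

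**Method A: a gap in means.** If those not retested score g points below those retested, the experimental mean is inflated by (m/18) × g.

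| m lost | g = −8.55 | g = 0 | g = 8.55 (0.5 SD) | g = 17.1 (1 SD) |
|---|---|---|---|---|
| 2 | −0.95 | 0 | 0.95 | 1.90 |
| 3 | −1.43 | 0 | 1.43 | 2.85 |

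A negative g means that absentees do better, and the sign of the bias reverses.

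**Method B: a correlation.** Let rho be the correlation between propensity to attend and post-test score, and let the m lowest on propensity be lost. Then bias = rho × 17.1 × S(m)/(18 − m). S(m) is the sum of the absolute values of the m lowest expected normal order statistics for n = 18 (1.820, 1.350, 1.066, ...).

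- m = 2: S = 3.170 and 3.170/16 = 0.198. Bias is 1.0 points at rho 0.3 and 1.7 at rho 0.5, or 7% and 12% of 13.7.
- m = 3: S = 4.236 and 4.236/15 = 0.282. Bias is 1.4 and 2.4 points, or 11% and 18% of 13.7.
- m = 6 (one third of the arm, well beyond the planned loss): S = 6.251 and 6.251/12 = 0.521. Bias is 2.7 and 4.5 points.
- rho = 0: no bias at any m.

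**False favourable significance.** I simulated 40,000 trials per scenario with no true effect, 18 complete controls and an independent t test at two-sided 5%. The nominal favourable rate is 2.5%. It becomes about 4.0% and 4.6% for 2 lost (rho 0.3 and 0.5), and about 4% and 6% for 3 lost.

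**Loss in controls too.** One control lost by the same mechanism inflates the control mean by rho × 17.1 × 1.820/17, which is 0.55 points at rho 0.3 and 0.92 at rho 0.5. With 3 experimental adolescents lost, the net bias falls to 0.9 and 1.5 points. Equal loss of the same kind cancels it. If 2 are lost from the experimental arm and 3 from the control arm, it reverses: 1.02 − 1.45 = −0.4 points at rho 0.3.

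**Power.** For the two-sided independent t test at effect size 0.8, power is 64.5% with 18 v 18, 61.7% with 16 v 18 and 60.1% with 15 v 18. Complete retesting therefore also recovers a little precision.

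**The case against.** The text says when the scales are given; it does not say that absentees are left out. A sensible investigator might well telephone them. A reader might infer that the plan compares programme completers with all controls and is therefore biased towards the intervention. The documents do not support that reading, for four reasons.

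- Even read literally, a between-group score needs presence at session six only, and a paired change needs sessions one and six. An adolescent who missed the sessions in between would still be measured.
- Complete control follow-up is nowhere promised. Controls receive no intervention during the study and no described reminder calls, so they may be lost as often as the experimental arm, or more often. The allowance for loss was applied to both arms.
- The direction is not known. Adolescents who are doing well may also skip weekend meetings.
- The arithmetic covers the between-group comparison of quality-of-life level. It does not carry over directly to the within-arm paired tests, or to the coping scale, whose avoidant and negative subscales have no single direction of benefit.

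All of this stands, and it limits the claim. It does not remove the gap. The plan fixes the time and setting of the only experimental post-test, expects losses, and states no way to obtain a score from someone who is not there. The attendance condition applies to one arm, even though loss itself may not.

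**Conclusion.** The gap is real and should be fixed, but it is a risk of bias and not a demonstrated one. Outcome collection depends on attendance in the experimental arm and on calendar time in the control arm, with no provision for absentees or for missing post-tests. Differential loss of unknown size and direction cannot be excluded.

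At the loss the plan itself expects, the bias is modest: about 1.0 to 1.7 points with 2 of 18 lost, and about 1.4 to 2.4 points with 3 lost. These figures assume rho between 0.3 and 0.5, SD 17.1 and no control loss. No figure in the documents fixes rho.

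**What to change.** **Protocol section 1.4.** State that every randomised adolescent in both arms completes the three scales at the post-test, however many sessions they attended. Anyone absent from session six is telephoned and completes the scales face to face at a separate contact. Use the same reminders in both arms. The place of the control retest should be stated as well, because the outpatient clinic is named only for the control pre-test.

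**Timing.** The same section gives both a three-month duration and one-week spacing for six sessions. Weekly spacing would put session six about five weeks after session one, against three months for the control retest. These statements must be reconciled so that the post-test falls at the same time in both arms.

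**Statistical Analysis.** Analyse everyone with a post-test in the arm to which they were allocated, and report the number without a post-test by arm.

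**Cost.** Some rewording, plus a telephone call and a short questionnaire contact for the few who miss session six. Telephone contact is already part of the plan, and the protocol puts the quality-of-life scale at 5 to 10 minutes. Enrolment stays at 18 + 18. The estimated effect may be slightly smaller because non-attenders are counted.

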
It has been determined that there are no studies in the literature on peer interactive group support on celiac adolescents. In line with this information, it was planned to examine the effect of peer interactive group support to be given to adolescents with celiac disease in the 13-18 age group on the quality of life, peer relationships and coping levels of adolescents.

3. Materials and Methods of the Research:

3.1. Location of the study: The research will be carried out in Afyon Kocatepe University Hospital (Afyonkarahisar) Child Health and Diseases Polyclinic. (Institution permit certificate is attached.)

3.2. Time of study: The research will be conducted between June 2018 and December 2018.

3.3. The population, sample, and research group of the study: In the province of Afyonkarahisar where we planned to study, the incidence rate of the disease was shown to be 0.05% according to 2015 data and it was stated that there were 322 patients (77). There are 85 patients with a diagnosis of celiac disease in the 0-18 age group who were followed up in the Afyon Kocatepe University Pediatric Outpatient Clinic where the

study will be conducted. There are 36 patients with a diagnosis of celiac disease in the 13-18 age group. Patients with a diagnosis of celiac disease in the 13-18 age group who are followed up in the Child Health and Diseases outpatient clinic of Afyon Kocatepe University will constitute the universe of the study.

Research inclusion criteria;

- Agree to participate in research
- Being a patient diagnosed at least a year ago
- Being a boy or a girl in the 13-18 age group
- No other chronic illness or psychiatric disorder
- Not being in the hospital while working

There will be two groups in the study, namely the experimental and the control group. While peer interactive group support is applied to the experimental group, no intervention will be made to the control group.

Since the study was experimental, the sample size was determined by power analysis.

Sample Number Calculation

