 - What is gluten?
 - What are edible foods for people with celiac disease?
 - What foods should celiac patients avoid?

- What should celiac patients pay attention to in their diet?
Food shopping and reading labels for people with celiac disease
- Alternative solutions, food suggestions
- Living gluten-free in school, home and social life will be covered.

After the research is completed, the control group will also be given training on celiac disease and a training booklet titled "Living with Celiacs" to be prepared by the researcher will be given..

DATA COLLECTION TOOLS

INTRODUCTORY INFORMATION FORM FOR DIAGNOSED ADOLESCENTS

The introductory information form for adolescents with a diagnosis of celiac disease was created by the researcher. It consists of 14 multiple choice questions in total.

QUALITY OF LIFE SCALE FOR CHILDREN

The quality of life scale for children is a quality of life scale developed in 1999 as a result of a 15-year study by Varni et al. In order to measure the health-related quality of life of children and adolescents between the ages of 2 and 18 (78). Children's health-related quality of life measurement is used to determine the risks of their diseases, to evaluate their health status subjectively, to monitor the results of the treatment and to make comparisons. The Turkish validity and reliability study of the scale for 13-18 years old was carried out by Nursu Çakın Memik et al. In 2005. The scale has sub-dimensions consisting of physical health, emotional functionality, social functionality and school functionality (79). The quality of life scale for children consists of 23 items. Physical health consists of 8 items, emotional functionality 5, social functionality 5, and school functionality 5 items. Scoring is done in 3 areas. First, the total score of the scale (STP) (23 items), secondly the physical health total score (FSTP) (8 items), and the third, the psychosocial health total score (PSTP), which consists of calculating the item scores evaluating emotional, social and school functionality (15 item) is calculated (80). The Cronbach alpha coefficient of this study was 0.82 in the adolescent form. With this study, it was determined that the 13-18 year-old adolescent forms of the "Children's Quality of Life Scale" are valid and reliable in our country and can be used to evaluate the health-related quality of life of adolescents (79).

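### The experimental arm gets the booklet when group support ends, and nothing ensures that controls have had their post-test by then

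*Combined protocol and SAP*

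**What the plan says.** The protocol's section on research method and data collection tools (numbered 1.4) runs three separate clocks.

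- **Booklet, experimental arm.** "After peer interactive group support, celiac patients will be given an educational booklet named 'Living with Celiacs' to be created by the researcher". No date or week is given. The patients meant are most naturally the experimental arm, because the control group is dealt with separately.
- **Booklet, control arm.** "After the research is completed, the control group will also be given training on celiac disease and a training booklet". Section 3.3 adds that "no intervention will be made to the control group".
- **Control post-test.** "After three months, the Adolescents in the control group will be re-administered the Quality of Life Scale for Children". The three months run from a pre-test taken in the outpatient clinic, whose date is not tied to session one or session six.

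The experimental arm is pre-tested at session one ("In this session, Introductory Information Form, Children's Quality of Life Scale, Peer Relationship Scale, Adolescent Coping Scale will be applied to Adolescents with Celiac Diagnosis") and post-tested when the programme closes ("At the end of the sixth session, the Adolescents will be again applied to the Quality of Life Scale for Children"). The length and spacing of the programme are given in one sentence: "Peer interactive group training will be applied for 3 months, one week apart, and will consist of 6 sessions in total".

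The study takes place in one hospital outpatient clinic (section 3.1). All 36 of its patients aged 13 to 18 are in the sample, and they are allocated individually by lottery (Statistical Analysis, sample number calculation). Neither document describes a step to prevent sharing between arms.

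**The concern.** By holding the booklet back from controls until the research is over, the plan itself treats it as material that should not precede their measurement. That protection applies only to booklets handed directly to controls. The experimental arm's copies are released on a different trigger, the end of group support, which is not checked against the control assessments.

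A printed booklet is easy to pass on. Its listed contents (food shopping and labels, food alternatives, managing at school, at home and socially) bear on the daily-life difficulties that the sessions address. A control who read it before the post-test would have had part of what the plan withholds. If the booklet helps, control scores rise and the between-arm difference shrinks. No question about exposure to the booklet is described, so this could not be separated out afterwards.

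**Working it through.** The plan gives no hand-out date and no interval between hand-out and control post-test, so there is no figure of its own to reproduce. The interval has to be derived from the schedule.

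**Inputs from the protocol, section on research method:** six sessions; a programme described both as three months long and as having sessions one week apart; experimental post-test at the end of session six, then the booklet; control post-test three months after the control's own pre-test.

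**Conversion:** three months = 365.25 / 12 × 3 / 7 = 13.04 weeks.

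**Formula.** Let g be the weeks between sessions, with session one at week 0. Session six, and so the earliest booklet hand-out, falls at week 5g. Let s be the week of a control's pre-test relative to session one, positive if later. The control post-test falls at week s + 13.04. Then

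gap = s + 13.04 − 5g,

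where a positive value means that the booklet is out before that control is measured.

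| Reading of the schedule | g (weeks) | Session six (week) | Gap with common start (s = 0) |
|---|---|---|---|
| Weekly sessions | 1 | 5 | 13.04 − 5 = 8.04 weeks |
| Fortnightly sessions | 2 | 10 | 13.04 − 10 = 3.04 weeks |
| Sessions spanning the full three months | 13.04 / 5 = 2.61 | 13.04 | 0 |

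The two statements about the programme cannot both be literal: six sessions a week apart finish at week 5, not week 13.

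**Effect of the control start date.** The term s adds directly to the gap. In the third row, every control pre-tested after session one is still measured after the booklet is out. In the other direction, the order reverses for a control pre-tested more than 3.04 weeks before session one (fortnightly row) or more than 8.04 weeks before it (weekly row). The documents fix neither case.

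**Recall window.** The quality-of-life scale asks about the last month (protocol, description of that scale). A 3-week gap would lie within that month, and an 8-week gap would cover all of it.

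**Size of any bias.** If a fraction p of controls sees the booklet early and each gains b points, the between-arm difference falls by p × b. The documents supply neither p nor b.

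**The case against.** The strongest reply is that the same three-month figure appears for the programme and for the control re-test, which suggests that the two post-tests were meant to coincide. On that reading the gap is 0 with a common start. This stands in part. A reader might infer that the plan sets the hand-out before the control post-test; it does not. The order is possible, not stated. Coincidence is not secured either, because the control pre-test has no anchor.

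A reader might also infer that the booklet contaminates the experimental arm's own post-test. The text does not support that. Those forms belong to the end of session six, and the booklet comes after the support has finished.

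It is tempting to put a number on the dilution. The planned gain is 82.8 − 69.1 = 13.7 points. Assume that 2 to 6 of 18 controls are exposed and gain a quarter to a half of it: the loss is 2/18 × 0.25 × 13.7 = 0.4 points to 6/18 × 0.5 × 13.7 = 2.3 points, or 3% to 17%. Both inputs are invented, and 13.7 points is the target for six group sessions, not for a leaflet. Even the upper figure is about 0.4 of the standard error of the difference, 17.1 × √(2/18) = 5.7 points. The range illustrates the arithmetic and is not an estimate.

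Sharing itself is inferred. The experimental arm meets at weekends, controls complete their first forms in the clinic, and no contact between arms is described. Session one also covers what celiac disease is, its symptoms and its treatment, so similar information could pass by word of mouth whatever the booklet's timing. Both points are fair and keep the severity low.

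Finally, it can be said that the real fault is the schedule conflict. Reconciling it would narrow the gap. It would not by itself protect a control who was pre-tested after session one.

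**Conclusion.** The point holds as a gap in sequencing. As written, the plan allows material withheld from controls to be released before some of them are measured. With a common start the interval is 0 to about 8 weeks, depending on how the session schedule is read. It is longer for controls who start later than session one, and shorter or reversed for those who start earlier.

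The consequence is conditional on booklets being shared across arms and on the booklet improving scores. If both hold, the bias runs toward no effect; it would not create a false positive in favour of group support. Its size cannot be estimated from the documents. Severity is low, and the case for acting rests on how little the change costs.

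**What to change.** In the protocol's section on research method, replace the experimental arm's booklet trigger with a common one: the booklet is given to either arm only after the last post-test in both arms has been completed. This removes the booklet route under every reading of the schedule.

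Separately, reconcile the stated programme length and session spacing with each other and with the date of the control post-test. Which spacing was intended is for the study team to state.

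The cost is a delay for the experimental arm equal to the gap to the last control post-test: 0 to about 8 weeks with a common start, longer if some controls are pre-tested late. The same patients receive the same booklet, and no sample size, assessment or analysis changes. The change does not prevent session content from passing by word of mouth.

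The statistical section is written in the past tense. If the booklets have already been handed out, what remains is to report the hand-out dates alongside the dates of the control post-tests.
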